Investigator, there is a logical connection between the use of the device and the occurrence of the event, above and beyond the study procedure itself. Examples include:

- Optimizer lead failure (dislodgement, fracture) requiring surgical revision
- Optimizer IPG failure requiring surgical revision
- Optimizer pocket erosion requiring surgical revision
- Pocket stimulation secondary to CCM, requiring surgical revision

C. Procedures for recording and reporting adverse events and intercurrent illnesses.

The Investigator shall report all adverse events to Impulse Dynamics and to the reviewing IRB (according to Hospital policy). All device malfunctions and serious adverse events, including, but not limited to events associated with prolongation of hospitalization, and/or a new hospitalization or death shall be reported to Impulse Dynamics within 24 hours of the Investigator learning of the event. Impulse Dynamics will report serious adverse events to the Data Safety and Monitoring Board (during the 1 year study only) and to the FDA as required.

D. Type and duration of follow-up of subjects after adverse events.

All subjects experiencing serious adverse events will be followed as required by their condition. Impulse Dynamics will investigate any anticipated or unanticipated serious adverse effect or subject death. If it is determined that the adverse event could present an unreasonable risk to other subjects, all investigations or parts of investigations presenting that risk will be terminated. Investigation of the event and notification of study termination will occur within five working days after notice of the effect is received at Impulse Dynamics. The terminated investigation will not be resumed without IRB approval.

IX. Statistical Considerations

A. Description of the statistical methods to be employed

1. Primary efficacy analysis

The primary efficacy analysis will compare responder rates between the Treatment and Control groups at the 6-month follow-up visit. The primary outcome measure will be:

- change from baseline in the ventilatory threshold (VT) determined on cardiopulmonary stress testing

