Individual patient response will be defined as an increase of ≥ 1 **ml O₂/kg/min** in VT at 6 months as compared with baseline. Responder rates will be calculated and compared between the treatment and control groups based on both the intent-to-treat population and the per-protocol population using a one-sided binomial comparison with an alpha of 0.025.

The statistical hypothesis to be tested is:

$$H_0: \pi_c \geq \pi_t \quad \text{vs.} \quad H_A: \pi_c < \pi_t$$

Where π_c is the proportion of patients in the control group that have ≥ 1 ml O₂/kg/min improvement in VT at 6 months from baseline and π_t is the proportion of patients in the treatment group that have ≥ 1 ml O₂/kg/min improvement in VT at 6 months from baseline.

2. Primary Safety Analysis

The primary safety analysis shall evaluate the composite event rate of all cause mortality and all cause hospitalization at 12 months. The statistical hypothesis shall be that the proportion of patients in the treatment group where an event occurs by 12 months will be non-inferior to the proportion of patients where an event occurs by the 12 month visit in the control group.

The statistical hypothesis to be tested shall be:

$$H_0: \pi_t > \pi_c + \delta$$

vs.

$$H_1: \pi_t \leq \pi_c + \delta$$

where $\delta=0.125$ (clinically insignificant difference) and π_c is the event rate in the control group and the π_t is the event rate in the treatment group.

The statistical test to be used shall be the Blackwelder non-inferiority test and will be evaluated based on the intent-to-treat patient population and the per protocol patient population. Censoring is expected to be minimal, but in order to determine if there are different patterns of mortality between groups, Kaplan-Meier curves will also be constructed, with Log-rank tests used to determine statistical significance between groups.

The nature, frequency, and seriousness of adverse events between the two groups shall be compared using descriptive summary statistics.

3. **Justification of sample size**

Results of prior studies of CCM and biventricular pacing in which VT has been employed as an endpoint provide estimates for standard deviations of changes and standard deviations of absolute values that may be observed in the present study.

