⁴ A difference in VT of 1 ml O₂/kg/min is justified as being clinically significant based on prior studies of cardiac resynchronization therapy showing that there is an approximately 1 ml O₂/kg/min change in response to that approved therapy (Auricchio et al. J Am Coll Cardiol 2003;42:2109-16)

The secondary analyses will include:

- a. Comparison between groups of the change from baseline in New York Heart Association (NYHA) classification. NYHA classification shall be assigned by:
 - i. blinded on site clinicians according to their standard clinical practice
 - ii. by a blinded core lab that evaluates patient responses to a standardized questionnaire.⁵
- b. Comparison between groups of the changes from baseline in quality of life, as assessed by the Minnesota Living with Heart Failure (MLWHF) Questionnaire.
- c. Comparison between groups of the change from baseline in exercise tolerance, as quantified by the six minute hall walk test (6MW).
- d. Comparison between groups of the change from baseline in left ventricular ejection fraction as assessed by echocardiography in a blinded core lab.
- e. Comparison between groups of the change from baseline in left ventricular size as indexed by echocardiographically determined end-diastolic dimension determined by a blinded core lab.
- f. Comparison between groups of the change from baseline in peak VO₂ and ventilatory efficiency determined on CPX testing.
- g. Comparisons of treatment effects separately in subjects whose CHF etiology is ischemic or non-ischemic
- h. Comparison between groups of the change from baseline in medical treatment for heart failure (either up or down titration of doses or changes in the types of medications prescribed).

⁵ **Kubo SH, Schulman S, Starling RC, Jessup M, Wentworth D and Burkhoff D.** Development and validation of a patient questionnaire to determine New York Heart Association classification. *J Card Fail* 10: 228-235, 2004.

- i. Comparison within the treatment group of the primary and secondary safety and efficacy outcome measures in subjects with and without a pacemaker or ICD.
 - j. Evaluation of the impact of CCM voltage on primary and secondary efficacy and safety outcome measures.
5. Other Analyses

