A comparison of the baseline characteristics between patients with missing data for the primary effectiveness variable and those without missing data are provided below. These test are intended to determine if there is evidence of not missing at random and if there is, to provide a remedy such that the missing data can be assumed to be missing at random for those patients for which imputation is planned. An initial analysis indicated that baseline weight, BMI, and site and core laboratory exercise durations were statistically significant. The weight variable was considered of lower importance, but the exercise duration could impact anaerobic threshold (AT, the primary effectiveness variable) and therefore indicated that, strictly speaking, the data are not missing at random. A review of the data indicated that the vast majority of exercise times exceeded 6-7 minutes and that subjects with short exercise times were less likely to show an improved AT regardless of treatment group. On that basis, any patient missing the 24 week PVO2 and/or 24 week AT was assigned a worst case score. This is similar to patients who had an event, i.e, patients who died or had an intervention (LVAD, heart transplant, or surgery to correct CHF) at a time that could be considered the reason why the data for 24 weeks was missing. There were 10 Active and 4 Control patients who had events prior to the 24 week visit and there were 3 Active and 6 Control patients who had an event between 24 and 50 weeks such that the event was considered the reason for missing the 24 week CPX. The inclusion of patients with missing 24 week data and a baseline core laboratory exercise time of less than 6.5 minutes results in 5 Active and 8 Control patients added to the worst score assignment list. The cumulative result is that 18 Active and 18 control patients had either the lowest AT value from any previous visit assigned, or if all AT values were missing for previous visits, the lowest AT value recorded for any randomized patient. These patients are indicated in Table IX.1 below as Imputation Case 6.

After removing the 13 cases with missing 24 week data and an exercise time less than 6.5 minutes, the baseline characteristic comparison between patients with missing and non-missing data at 24 weeks or baseline are presented in the following tables.

Table VIII.1 Baseline Demographics – Quantitative Variables - Compare Patients with Missing 24 Week AT data with those Not Missing 24 Week Data

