Baseline NYHA (Site)	0.0779
Baseline NYHA by Optimizer Treatment Interaction	0.2845
Baseline NYHA (Site) (NYHA = 3 or Not)	0.0779
Baseline NYHA by Optimizer Treatment Interaction	0.2845
CHF Etiology	-- ²
CHF Etiology by Optimizer Treatment Interaction	-- ²
Baseline MLWHFQ	0.0445
Baseline MLWHFQ by Optimizer Treatment Interaction	0.2504
BMI	0.7600
BMI by Optimizer Treatment Interaction	0.8891
Race (White)	0.7382
Race by Optimizer Treatment Interaction	0.0506
PTCA or CABG	0.3363
PTCA or CABG by Optimizer Treatment Interaction	0.2056
Baseline Core Lab Exercise Duration	0.0912
Baseline Core Lab Exercise Duration by Optimizer Treatment Interaction	0.3932
Pseudo-Site	0.5091
Pseudo-Site by Optimizer Treatment Interaction	0.7444

¹Covariates with P-values ≤ 0.20 are allowed to enter the competition for the final model (bold face in table). If the interaction is not significant, the P-value reported is for the model with the main effect only.

²The model for CHF etiology did not have a solution so no P-value is reported.

The final model appears was determined by manual backward elimination and the result is presented in the table below. Eight variables were included in the competition for the final model including age, diabetes, baseline NYHA (continuous or categorical), baseline MLWHFQ, race, and race by treatment interaction.

Table 2.2.6 Multivariate Cox Regression Final Model Results for Mortality

Factor	Hazard Ratio	95% CL on HR	P-Value*
Race (White)	0.712	0.535-0.947	0.0197

The treatment term was the last term removed from the model and its P-value at removal was 0.1627. This analysis implies that the only covariate associated with the primary safety composite endpoint of all cause death or hospitalization is race with Caucasians having a lower risk of death or hospitalization than non-Caucasians. Stepwise regression was applied to provide a verification of this models and the same model resulted from that application.

XII. Primary Effectiveness Analysis

For the primary effectiveness analysis, imputation was necessary to obtain study outcomes for patients that did not have an endpoint at 24 weeks. The imputation was done by the methods described in Section IX above. Ten imputations for the ITT patients appear in the tables below. First the means are presented and then the responder analysis (with a responder defined a subject whose AT increased by $\geq 20\%$).

Table XII.1a Mean AT at Study Time Points

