Imputation	Time	Control Mean (SD) N Med (Min, Max)	Optimizer Mean (SD) N Med (Min, Max)	P-value
ITT1	Baseline	10.90 (2.29) 213 10.56 (4.10, 17.05)	10.89 (2.32) 215 10.60 (4.10, 16.92)	0.9840 ¹
	24 Week ³	10.74 (2.27) 213 10.78 (4.10, 19.61)	10.81 (2.44) 214 10.40 (4.10, 19.82)	0.7505 ¹
	24 Week Difference From Baseline	-0.15 (2.25) 213 -0.17 (-7.29, 9.34)	-0.08 (2.35) 215 -0.09 (-6.91, 9.17)	0.3670 ²
ITT2	Baseline	10.90 (2.26) 213 10.65 (4.10, 17.05)	10.87 (2.34) 215 10.59 (4.10, 16.92)	0.8966 ¹
	24 Week ³	10.74 (2.25) 213 10.72 (4.10, 19.61)	10.80 (2.49) 214 10.42 (4.10, 19.82)	0.7855 ¹
	24 Week Difference From Baseline	-0.16 (2.25) 213 -0.17 (-5.68, 9.34)	-0.08 (2.29) 215 -0.11 (-6.55, 8.94)	0.3484 ²
ITT3	Baseline	10.92 (2.28) 213 10.72 (4.10, 17.05)	10.88 (2.30) 215 10.60 (4.10, 16.92)	0.8576 ¹
	24 Week ³	10.79 (2.28) 213 10.61 (4.10, 19.61)	10.78 (2.46) 214 10.40 (4.10, 19.82)	0.9688 ¹
	24 Week Difference From Baseline	-0.12 (2.27) 213 -0.17 (-6.10, 9.34)	-0.09 (2.29) 215 -0.09 (-6.47, 8.94)	0.4444 ²
ITT4	Baseline	10.90 (2.27) 213 10.73 (4.10, 17.05)	10.88 (2.29) 215 10.59 (4.10, 16.92)	0.9382 ¹
	24 Week ³	10.72 (2.30) 213 10.53 (4.10, 19.61)	10.81 (2.51) 214 10.42 (4.10, 19.82)	0.3122 ¹
	24 Week Difference From Baseline	-0.19 (2.27) 213 -0.12 (-6.03, 9.34)	-0.08 (2.35) 215 -0.09 (-6.47, 8.94)	0.6878 ²
ITT5	Baseline	10.93 (2.28) 213 10.73 (4.10, 17.05)	10.89 (2.30) 215 10.59 (4.10, 16.92)	0.8492 ¹
	24 Week ³	10.69 (2.31) 213 10.53 (4.10, 19.61)	10.81 (2.42) 214 10.49 (4.10, 19.82)	0.6081 ¹
	24 Week Difference From Baseline	-0.24 (2.19) 213 -0.13 (-8.59, 9.34)	-0.08 (2.28) 215 -0.09 (-6.88, 8.94)	0.2390 ²
ITT6	Baseline	10.89 (2.27) 213 10.65 (4.10, 17.05)	10.87 (2.29) 215 10.59 (4.10, 16.92)	0.9170 ¹
	24 Week ³	10.69 (2.28) 213 10.64 (4.10, 19.61)	10.74 (2.56) 214 10.39 (4.10, 19.82)	0.8389 ¹
	24 Week Difference From Baseline	-0.21 (2.23) 213 -0.17 (-5.13, 9.34)	-0.14 (2.41) 215 -0.14 (-8.23, 8.94)	0.3898 ²
ITT7	Baseline	10.88 (2.30) 213 10.65 (4.10, 17.05)	10.90 (2.33) 215 10.60 (4.10, 16.92)	0.9253 ¹
	24 Week ³	10.81 (2.29) 213 10.80 (4.10, 19.61)	10.78 (2.46) 214 10.42 (4.10, 19.82)	0.9088 ¹
	24 Week Difference From Baseline	-0.07 (2.32) 213 -0.10 (-6.65, 9.34)	-0.12 (2.33) 215 -0.07 (-7.99, 8.94)	0.5948 ²
ITT8	Baseline	10.95 (2.28) 213 10.73 (4.10, 17.05)	10.83 (2.33) 215 10.59 (4.10, 16.92)	0.5965 ¹
	24 Week ³	10.68 (2.27) 213 10.53 (4.10, 19.61)	10.70 (2.49) 214 10.38 (4.10, 19.82)	0.9248 ¹

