	24 Week Difference From Baseline	-0.27 (2.23) 213 -0.22 (-6.71, 9.34)	-0.13 (2.40) 215 -0.16 (-6.91, 8.94)	0.2711 ²

Table XII.1a Mean AT at Study Time Points (Continued)

Imputation	Time	Control Mean (SD) N Med (Min, Max)	Optimizer Mean (SD) N Med (Min, Max)	P-value
ITT9	Baseline	10.94 (2.28) 213 10.73 (4.10, 17.05)	10.89 (2.30) 215 10.59 (4.10, 16.92)	0.8402 ¹
	24 Week ³	10.72 (2.21) 213 10.72 (4.10, 19.61)	10.80 (2.50) 214 10.40 (4.10, 19.82)	0.7000 ¹
	24 Week Difference From Baseline	-0.22 (2.14) 213 -0.23 (-5.04, 9.34)	-0.08 (2.26) 215 -0.14 (-6.51, 8.94)	0.2645 ²
ITT10	Baseline	10.89 (2.28) 213 10.56 (4.10, 17.05)	10.88 (2.29) 215 10.57 (4.10, 16.92)	0.9462 ¹
	24 Week ³	10.69 (2.33) 213 10.64 (4.10, 19.61)	10.79 (2.45) 214 10.46 (4.10, 19.82)	0.6547 ¹
	24 Week Difference From Baseline	-0.21 (2.34) 213 -0.13 (-8.59, 9.34)	-0.08 (2.25) 215 -0.17 (-6.47, 8.94)	0.2845 ²

¹Two-sided equal variance Student's t-test.

²One-sided equal variance Student's t-test

³One patient in the Optimizer group had a difference imputed but did not have a 24 week AT imputed.

The responder analysis for the 10 imputations appears below.

Table XII.1b Univariate Primary Effectiveness Endpoint Results (≥20% Improvement) for ITT Patients

Population	Control n/N (%)	Optimizer n/N (%)	P-value ¹
ITT1	28/213 (13.15)	37/215 (17.21)	0.1500
ITT2	31/213 (14.55)	37/215 (17.21)	0.2681
ITT3	29/213 (13.62)	38/215 (17.67)	0.1533
ITT4	26/213 (12.21)	39/215 (18.14)	0.0573
ITT5	27/213 (12.68)	40/215 (18.60)	0.0598
ITT6	26/213 (12.21)	36/215 (16.74)	0.1157
ITT7	30/213 (14.08)	36/215 (16.74)	0.2652
ITT8	24/213 (11.27)	39/215 (18.14)	0.0304
ITT9	27/213 (12.68)	40/215 (18.60)	0.0598
ITT10	33/213 (15.49)	38/215 (17.67)	0.3169

¹One-sided Fisher's exact test

Rubin (1987) indicates that the data from multiple imputations can be combined to get an overall test of significance. The method is the basis of Proc MIANALYZE in SAS and is described in the online manual SAS OnlineDoc Version 8, Chapter 10 (Proc MIANALYZE), page 211.

The procedure computes the mean difference across all imputations by the following formula

$$\bar{Q} = \frac{1}{m} \sum_{i=1}^m \hat{Q}_i$$

where Q_i is the difference between the Optimizer proportion and the control proportion for the i th imputation and m is the number of imputations ($M=10$ here)

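### Section XII of the statistical report tests the 24-week AT change ten times per population and pools only responder proportions, so AT change has no pooled between-arm difference or interval.

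*Combined protocol and SAP*

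**What the plan says.** Protocol Section IX.A.1 names the primary outcome measure as "change from baseline in the ventilatory threshold (VT) determined on cardiopulmonary stress testing". The planned test compares responder rates by a "one-sided binomial comparison with an alpha of 0.025". Footnote 4 to Section IX.A.3 says that a VT difference of 1 ml O2/kg/min "is justified as being clinically significant based on prior studies of cardiac resynchronization therapy".

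The Statistical Analysis Report calls the variable AT and describes it in Section VIII as "anaerobic threshold (AT, the primary effectiveness variable". On layout, Section XII says "First the means are presented and then the responder analysis", and "Ten imputations for the ITT patients appear in the tables below". Tables XII.1a to XII.9a give arm means, SDs and a separate P-value for AT at baseline, at 24 weeks and as change, once per imputation. After Table XII.1b the report sets out Rubin's combination formulas, with the pooled quantity defined as the difference between arms in the responder proportion. Each population or sub-group then receives one combined z and P, placed after its responder table. No combined result for the mean change appears.

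**The concern.** A t-test on one completed data set treats imputed values as if they had been observed. By Table IX.1, 159 + 153 = 312 of 428 patients had complete data, so 116 contribute at least one imputed or assigned value. The report allows for the resulting uncertainty in the responder rates but not in the means. The reader therefore sees ten P-values for one question, and in EF>=25 they fall on both sides of the 0.025 level. The size of the effect on the variable that the report calls primary, with its uncertainty, cannot be read from any table. Two P-values in the ITT4 block of Table XII.1a also disagree with the means and SDs beside them.

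**Working it through.** **Method.** The report's own formulas with m = 10: Q is the average over imputations of (Optimizer mean change minus Control mean change); U is the average squared equal-variance standard error; B is the variance of the ten differences; T = U + 1.1 x B; SE = square root of T. Intervals are Q +/- 1.96 x SE and P is one-sided. Inputs are the rows for 24-week difference from baseline in Tables XII.1a to XII.3a (ITT), XII.4a (FASA) and XII.7a (FASB).

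**What the report's combined z-values pool.** For ITT with EF>=25 and NYHA=3, the responder counts in Table XII.3b give Q = 0.1209, U = 0.00242, B = 0.00039, T = 0.00285 and z = 0.1209/0.0534 = 2.26. This matches the printed 2.2624 apart from sign. The mean changes for the same patients give 1.99, so the combined values are responder pools. The whole-ITT z of -0.4839 reproduces from neither source: responders give 1.15 and means give 0.38. That is a separate matter to check.

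**Whole ITT, step by step.** The ten differences are 0.07, 0.08, 0.03, 0.11, 0.16, 0.07, -0.05, 0.14, 0.14 and 0.13, so Q = 0.088. U = 0.0488 and B = 0.0040, so T = 0.0488 + 1.1 x 0.0040 = 0.0532 and SE = 0.231. The interval is 0.088 +/- 1.96 x 0.231.

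| Set | Q | U | B | SE | 95% CI | P |
|---|---|---|---|---|---|---|
| ITT | +0.088 | 0.0488 | 0.0040 | 0.231 | -0.36 to 0.54 | 0.35 |
| FASA | +0.074 | 0.0503 | 0.0034 | 0.233 | -0.38 to 0.53 | 0.38 |
| FASB | +0.029 | 0.0501 | 0.0030 | 0.231 | -0.42 to 0.48 | 0.45 |
| ITT, EF>=25 | +0.585 | 0.0890 | 0.0089 | 0.314 | -0.03 to 1.20 | 0.031 |
| ITT, EF>=25 and NYHA=3 | +0.648 | 0.0995 | 0.0062 | 0.326 | 0.01 to 1.29 | 0.023 |

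Rubin's t reference distribution (about 1,320 degrees of freedom for ITT) changes nothing material.

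**Understatement of the standard error (1 minus square root of U over SE).** Whole ITT: 1 - 0.221/0.231 = 4%. EF>=25: 1 - 0.298/0.314 = 5%. EF>=25 and NYHA=3: 1 - 0.3155/0.326 = 3%.

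**Spread of the printed P-values, ITT EF>=25 (Table XII.2a).** Below 0.025: 0.0152, 0.0106, 0.0203, 0.0124, 0.0112. Above: 0.0374, 0.0533, 0.0328, 0.0876, 0.0314. The pooled value is 0.031.

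**Distance from 1 ml/kg/min, whole ITT.** (1 - 0.088)/0.231 = 3.95 standard errors. No single imputation has an upper limit above 0.58. For the pooled interval to reach 1, B would have to be about 0.152, some 38 times its value. Completed cases (Table XIII.1a) agree: -0.14 in both arms, difference 0.00, SE = square root of (2.14^2/154 + 2.23^2/159) = 0.247, interval -0.48 to 0.48.

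**ITT4 rows, Table XII.1a.** Change: -0.08 - (-0.19) = 0.11, SE 0.2234, t = 0.49, one-sided P = 0.311; the table prints 0.6878. Week 24: 10.81 - 10.72 = 0.09, SE 0.233, t = 0.39, two-sided P = 0.70; the table prints 0.3122. The two printed values sum to 1, which suggests a wrong tail and a misplaced entry.

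**The case against.** The planned comparison is between responder rates, and the report pools those for every population and sub-group. The means are supporting displays, and not pooling them departs from no stated plan. This stands, and it limits the point to a supporting estimate.

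A reader might infer that the trial gives no estimate at all for its primary variable, or conceals a null result. The documents do not support that. Arm means and SDs are printed for every imputation, the completed-case change is -0.14 in both arms with P = 0.5040, and the text says that the whole population does not reach significance. What is missing is a pooled between-arm difference and any interval.

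A reader might also infer that favourable single P-values were selected. The closing paragraph of Section XII relies only on the combined responder results; no conclusion there rests on a single-imputation t-test.

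The 1 ml/kg/min value is mainly an individual response cut-off, and the sample size was argued from responder rates. Footnote 4 nevertheless justifies it as a clinically significant VT difference by reference to an average change of about that size with an approved therapy. It is therefore a fair reference for a mean, though not a design effect.

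Finally, the pooled mean is not a clean effect size. Section VIII assigns 18 patients per arm, 36 in all, their lowest earlier AT or the lowest AT of any randomized patient. Table IX.2 uses fixed regression coefficients, so B may be too small. The 38-fold margin and the completed cases protect the whole-population reading. Nothing similar protects the sub-group P of 0.023, which becomes 0.030 in FASB (+0.631, -0.03 to 1.29).

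**Conclusion.** The point holds as a reporting gap that should be closed. AT change has no pooled between-arm difference or interval, and the printed P-values rest on standard errors 3-5% too small. The practical effect is clearest in ITT EF>=25, where half of the ten P-values fall below 0.025 and the pooled P of 0.031 does not. In the whole population the pooled difference is +0.09 ml/kg/min (-0.36 to 0.54), an interval wholly below 1; FASA, FASB and completed cases agree.

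Two stronger readings fail. The results do not exclude a mean effect of 1 ml/kg/min in the sub-groups, since both ITT intervals include it (upper limits 1.20 and 1.29). Nor does P = 0.023 in EF>=25 with NYHA=3 establish benefit: that sub-group is not among the endpoints or analyses listed in the protocol, there is no multiplicity adjustment, and the lower limit is 0.01.

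The figures rest on means and SDs printed to two decimals, the report's variance formula with actual arm sizes, and the report's imputations taken as given. The primary responder test is unaffected.

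**What to change.** Apply the report's combination formula to the mean 24-week AT change. Print one difference, 95% CI and one-sided P for each of ITT, FASA and FASB, as a supporting estimate beside the responder test. Note that the whole-population interval lies below the 1 ml/kg/min of footnote 4.

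Give the pooled sub-group results in the same table, labelled exploratory and unadjusted for multiplicity, and state that both ITT intervals include 1. Add a footnote that the means contain worst-case assigned values for 36 patients.

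Move the ten single-imputation P-values to an appendix. Correct the ITT4 rows of Table XII.1a to 0.311 (one-sided, change) and 0.70 (two-sided, week 24) after checking against the data.

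The cost is minutes of programming with existing data and code, and one summary table in place of nine in the main text.
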